5.3 DATA ANALYSIS GENERAL CONSIDERATIONS

5.3.1 Pooling of Centers

This study is a multicenter, international study with approximately 125 sites. Sites will be pooled into the following regions, in order to have sufficient number of subjects per treatment group:

- North America (USA & Canada)
- Western Europe (including the Oceania region)
- Asia (including Japan)

5.3.2 Adjustments for Covariates of Interest

The primary, secondary, and exploratory endpoints will include the stratification variables clinical subgroup (MCI due to AD, Mild Alzheimer's Disease Dementia), *APOE ε4 carrier status* (positive or negative) and the presence or absence of ongoing AD treatment (i.e., AChEIs and/or memantine). In addition, the following covariates of interest will be evaluated in the statistical models: Age (treated as continuous and as categorical age ≤ 65 , $65 < \text{age} < 80$, age ≥ 80 years), region and *APOE* alleles ($\epsilon 4/\epsilon 4$, $\epsilon 4/\text{other}$ and $\text{other}/\text{other}$)

5.3.3 Multiple Comparisons/Multiplicity

This study has one primary endpoint so no adjustment for multiplicity is required. The primary endpoint will be analyzed using a Bayesian Normal Dynamic Linear Model; therefore, no adjustment for multiplicity is required. Key secondary analyses compare the combined 10mg treatment groups with placebo, so there is no need to adjust multiplicity for multiple dose groups.

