5 STATISTICAL METHODS

In this Phase 2 dose-finding study of BAN2401 for the treatment of Early Alzheimer's Disease, response adaptive randomization will be used to allocate subjects to placebo control or 1 of the 5 active doses with the goal of characterizing the dose response. The study will be monitored for early success and early futility. The sponsor intends that the futility rule for stopping will be binding. If the study continues to randomize subjects after futility boundary has been crossed, it will be considered a failed study.

All statistical analyses for Core Study will be performed by the sponsor or designee. All of the Bayesian analysis will be conducted by an external IMC. The sponsor and investigators will be blinded to the IA data and outputs. The detailed processes and procedures related to study success at IA and the Bayesian analysis at 12 months are defined in a separate integrity charter. All other statistical analyses for Core Study will be performed by the sponsor or designee after the database is locked and released for unblinding. At each IA of the primary endpoint, a snapshot of the data will be obtained and released for analysis. A copy of this snapshot will be archived. This process will also be followed for the safety data that will be used for analysis for the DSMB. Statistical analyses will be performed using SAS software or other validated statistical software as required. All statistical tests for conventional analysis will be based on the two-sided 10% or one-sided 5% level of significance. The definition of success at primary analysis based on Bayesian methods is given in [Section 5.4.2 Adaptive Trial Definitions](#).

All descriptive statistics for continuous variables will be reported using mean, standard deviation (SD), median, minimum and maximum. Categorical variables will be summarized as number (percentage) of subjects.

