5.4.4 Secondary Efficacy Analyses

The Full Analysis Set will be used in secondary efficacy analyses.

Key Secondary Endpoint Analyses

Key Secondary endpoints and corresponding analyses are ordered to reflect the most recent FDA draft guidance (February, 2018) and EMA Final Guideline (February, 2018) that prioritize effects on pathophysiology in early AD, as measured by biomarkers. Conventional analysis will be performed using all available data at the time of success (if applicable), and at 18 months of treatment, regardless of success. As described in section 5.4.1.2, conventional analysis will be based on the MMRM model including baseline as covariate, with treatment group, visit, randomization stratification variables (i.e., clinical subgroup [MCI due to AD, Mild Alzheimer's Disease Dementia], the presence or absence of ongoing AD treatment [AChEIs or memantine or both], *APOE4* status [positive, negative]), region, treatment group-by-visit interaction as fixed effects. If there is an imbalance across treatment groups based on randomization stratification variables, additional MMRM model will be run without the randomization stratification variables. In addition, ANCOVA model will also be used with treatment as a factor and baseline value as a covariate. These statistical models will be used to compare the combined 10 mg dose group (including bi-weekly and monthly regimens) with placebo for the key secondary endpoints. The rationale for combining the two 10 mg dose regimens is to account for the loss of subjects positive for *APOE4* in the 10 mg/kg biweekly dose group and the inability to randomize *APOE4* carriers to the 10 mg/kg biweekly group following a regulatory request by European Health Authorities in July 2014.

In addition, analysis will be performed for the following treatment comparisons:

- Combining 2 high doses (10 mg bi-weekly + 10 mg monthly), 2 middle doses (5 mg bi-weekly + 5 mg monthly), and the 2.5 mg bi-weekly dose, resulting in 3 treatment comparisons with placebo (for dose response)
- ED₉₀ dose of BAN2401 versus placebo, where the ED₉₀ dose of BAN2401 will be established by Bayesian analysis at 18 months as described in the next paragraph
- By treatment regimen (10 mg bi-weekly, 10 mg monthly, 5 mg bi-weekly, 5 mg monthly, 2.5 mg bi-weekly, placebo)
- Combining the top 3 doses (10 mg bi-weekly, 10 mg monthly, and 5 mg bi-weekly) versus placebo

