For vMRI and amyloid PET endpoints, the adjusted p-value based on Dunnett-Hsu method with 1-sided alpha of 0.05 will also be provided in addition to the p-value corresponding to pairwise comparison.

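### The reason SAP 5.3.3 gives for not adjusting across dose groups does not cover the seven further dose contrasts that 5.4.4 tests for each key secondary endpoint

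*SAP*

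**What the plan says.** Section 5.3.3 rests its no-adjustment position for dose groups on one contrast: "Key secondary analyses compare the combined 10mg treatment groups with placebo, so there is no need to adjust multiplicity for multiple dose groups".

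Section 5.4.4, under Key Secondary Endpoint Analyses, names that contrast; the models are used to "compare the combined 10 mg dose group (including bi-weekly and monthly regimens) with placebo for the key secondary endpoints". It then lists four further sets of comparisons for the same endpoints:

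- three pooled dose levels, "resulting in 3 treatment comparisons with placebo (for dose response");
- the ED90 "dose of BAN2401 versus placebo", with the ED90 taken from the 18-month Bayesian analysis;
- each active arm singly, described as "By treatment regimen (10 mg bi-weekly, 10 mg monthly, 5 mg bi-weekly, 5 mg monthly, 2.5 mg bi-weekly, placebo"), which yields five separate tests;
- one wider pool, given as "Combining the top 3 doses (10 mg bi-weekly, 10 mg monthly, and 5 mg bi-weekly) versus placebo".

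The level comes from Section 5: "All statistical tests for conventional analysis will be based on the two-sided 10% or one-sided 5% level of significance". The only adjustment across regimens is at the end of 5.4.4: "For vMRI and amyloid PET endpoints, the adjusted p-value based on Dunnett-Hsu method with 1-sided alpha of 0.05 will also be provided", next to the unadjusted pairwise p-value. Section 4 defines the family for that method as five null hypotheses, one per active regimen.

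**The concern.** The argument in 5.3.3 works if one dose contrast per endpoint is tested. Section 5.4.4 tests several. It sets no order, makes none of them conditional on the combined 10 mg result, and does not say that they carry no significance claim.

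The plan is also uneven. For two imaging measures it treats the five regimens as a family needing adjustment. For the clinical scales and the CSF biomarkers the same five comparisons are left unadjusted, and no reason is given.

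At stake is how the 18-month results are read. A single regimen, or the top-three pool, could be reported as significant on ADCOMS or CDR-SB after the designated contrast has failed, while 5.3.3 tells the reader that dose multiplicity does not arise.

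**Working it through.** **Step 1. Count the contrasts for one endpoint (one model each).**

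| Set in 5.4.4 | Comparisons with placebo | New and distinct |
|---|---|---|
| Designated | combined 10 mg | 1 |
| Pooled dose levels | combined 10 mg, combined 5 mg, 2.5 mg biweekly | 2 (10 mg repeats) |
| By regimen | five regimens | 4 (2.5 mg repeats) |
| ED90 | one of the five regimens | 0 |
| Top three | pooled | 1 |

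Total 1 + 2 + 4 + 0 + 1 = 8, so seven beyond the designated one.

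**Step 2. Where adjustment applies.** Change at 18 months in amyloid PET and in total hippocampal volume are key secondary endpoints (5.1.2), and Section 4 powers or sizes the Dunnett-Hsu tests at 18 months for both. So 5.4.4 adjusts for multiple dose groups on key secondary endpoints for which 5.3.3 says this is unnecessary. The Dunnett-Hsu sentence follows the heading on other secondary endpoints. If it were confined to those, the key secondary regimen comparisons would have no adjustment at all, and the gap would be wider.

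**Step 3. Inputs for the size.** The SAP gives no family-wise error for these contrasts, so there is no figure to reproduce. Inputs: one-sided 5%, so a win is Z > 1.645; arm sizes from the Null row of simulation-plan Table 9.2: placebo 179.1, lowest biweekly 111.2 (labelled 3 mg there, taken here as the 2.5 mg arm), 5 mg biweekly 88.1, 10 mg biweekly 94.1, 5 mg monthly 106.6, 10 mg monthly 103.6.

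**Step 4. Formula.** For a regimen or pool S with n_S subjects and a sample-size-weighted mean,

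Z_S = (mean_S − mean_placebo) / (σ × √(1/n_S + 1/n_placebo)).

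The Z values are correlated because all share placebo and the pools overlap. For two single regimens i and j, the correlation is √[n_i n_j / ((n_i + n_0)(n_j + n_0))]. For the two 10 mg regimens it is √[94.1 × 103.6 / (273.2 × 282.7)] ≈ 0.36. The joint probabilities were obtained by simulating at least 400,000 sets of null arm means.

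**Step 5. Results: global null, one endpoint, wins in favour of drug.**

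| Event | Table 9.2 Null | 4:2:2:2:2:2 | Equal | 8:2:2:2:2:2 |
|---|---|---|---|---|
| Combined 10 mg wins | 5.0% | 5.0% | 5.0% | 5.0% |
| Any of five regimens | 18.6% | 18.8% | 16.6% | 20.6% |
| Any of seven further | 19.2% | 19.5% | 16.9% | 21.7% |
| Any of all eight | 19.5% | 19.7% | 17.1% | 22.1% |

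The first row checks the method, since one test returns its nominal 5%. Independent tests would give 1 − 0.95^8 = 33.7%, so the overlap between contrasts removes a good part of the inflation but not all of it.

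**Step 6. Added risk.** P(designated fails and another wins) = P(any of eight) − P(designated wins). With Table 9.2 sizes this is 19.5% − 5.0% = 14.5%; repeat simulations gave 14.4% to 14.5%. Equal allocation gives 17.1% − 5.0% = 12.1%, and 4:2:2:2:2:2 gives 19.7% − 5.0% = 14.7%. The placebo-heavy 8:2:2:2:2:2 case, a deliberate extreme, gives 22.1% − 5.0% = 17.1%.

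**Step 7. What adjustment would do.** Holding the five regimen tests at 5% overall needs a one-sided critical value of about 2.27 (p about 0.0116) instead of 1.645.

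**The case against.** The best defence is that one contrast is designated, with a stated rationale (the loss of APOE4 carriers from 10 mg biweekly), and the rest are extras introduced as additional analysis. Section 5.4.4 also speaks of sensitivity analyses above when it places the ED90 comparison, and the plural could be read to cover the whole list. Study success is defined on the 12-month Bayesian criterion alone, so none of these contrasts can make the trial a success. Dunnett-Hsu appears for imaging because the imaging calculations in Section 4 were built on it. A Phase 2 study need not control error over supportive displays.

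Much of this stands. The designated contrast's 5% error is not in dispute, and 5.3.3 nowhere says that combined 10 mg is the sole comparison made. The five regimens produce nearly all of the inflation; the extra pools add less than a point at the Table 9.2 sizes (18.6% to 19.5%).

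What does not stand is that the supportive status is already settled. The sensitivity label is clear only for the ED90 comparison, nothing withholds a significance claim from the others, and Section 5 assigns every conventional test a level. The Section 4 calculations explain where the imaging adjustment came from, but not why identical regimen comparisons on other key secondary endpoints go without it.

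A reader might also infer that regimen-level p-values choose the dose. The SAP does not support that: the ED90 is identified from Bayesian posterior probabilities at 12 months (5.4.1, 5.4.2) and again at 18 months (5.4.4).

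**Conclusion.** The point holds as a gap between a stated justification and the analyses it is meant to cover, together with unequal treatment of the same regimen comparisons across endpoints. For one clinical endpoint with no drug effect, the chance of at least one nominal win is about 19% at Table 9.2 Null sizes and about 17-22% over the allocations tried. The chance of a win elsewhere when combined 10 mg fails is about 14%, or about 12-15% across the equal, 4:2:2:2:2:2 and Table 9.2 allocations.

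These figures assume the global null, a normal approximation, fixed allocation and one model per contrast. The arm sizes are simulated means; the SAP does not give the final allocation, which was also shaped by the bar on APOE4 carriers in the 10 mg biweekly arm.

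Two stronger readings should be set aside. The combined 10 mg test is not inflated by the extra contrasts. Nor do these figures measure error across several endpoints: that would need between-endpoint correlations, which the SAP does not give, and is a separate question from dose contrasts within one endpoint.

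**What to change.** In 5.3.3, replace the last sentence with:

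> For each key secondary endpoint the significance claim rests on the combined 10 mg versus placebo contrast only; all other dose contrasts in 5.4.4 are supportive and carry no significance claim.

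In 5.4.4, provide the Dunnett-Hsu adjusted p-value beside the unadjusted one for the by-regimen comparisons of ADCOMS, CDR-SB, ADAS-Cog and the CSF biomarkers, as already planned for vMRI and amyloid PET.

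The first change closes the gap in the justification; the second makes the regimen tables consistent across endpoints. The cost is one sentence and one adjustment option in models already planned, with no new data. The downside is less favourable regimen-level p-values.

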5.3.4 Examination of Subgroups

The primary endpoint, key secondary endpoints, secondary endpoints and exploratory endpoints related to clinical assessments and biomarkers will be analyzed using the mixed-effects model with repeated measures to evaluate the following subgroups; age ≤ 65 , $65 < \text{age} < 80$, age ≥ 80 , gender, ethnicity, race, region, clinical subgroup (MCI due to AD, Mild Alzheimer's Disease Dementia), *APOE ε4 carrier status* (positive (overall, heterozygous and homozygous) or negative), and the presence or absence of ongoing AD treatment (i.e., AChEIs and/or memantine), subjects with/without neutralizing ADA, and biomarker subgroups defined in [Section 5.8](#).

5.3.5 Handling of Missing Data, Drop-outs, and Outliers

The missing primary endpoint will be imputed using Bayesian imputation method based on longitudinal model in the primary Bayesian analysis ([Section 5.4.2.2](#)). In the conventional analyses, the missing primary endpoint will be handled by the Mixed-effects Models for Repeated Measures (MMRM). Other statistical methods for missing data in conventional analyses may also be performed as sensitivity analyses. Missing values in key secondary endpoints, secondary endpoints and exploratory endpoints related to clinical assessments and biomarkers will be handled by the MMRM in the conventional analyses.

Efficacy Variables

If any item is missing within the Composite Score (ADCOMS), ADAS-cog, MMSE, CDR, and FAQ then their respective total scores will be missing.

CSF Biomarkers

Subjects with baseline values \geq ULOQ or \leq LLOQ will be excluded from all statistical analyses.

For analyses defined in [Section 5.8](#), only subjects with post-baseline values $>$ LLOQ and $<$ ULOQ will be included. For additional analyses, subjects with at least 1 post-baseline value,

including those \geq ULOQ or \leq LLOQ, will be categorized as follows: “stable”, “increased from baseline”, and “decreased from baseline”. For subjects that have numerical differences calculated, any increases will be categorized as “increased from baseline” and any decreases will be categorized as “decreased from baseline” regardless of magnitude. Difference of 0 will be categorized as “stable”. Subjects with baseline values $>$ LLOQ and $<$ ULOQ and post-baseline values \geq ULOQ will be categorized as “increased from baseline”, subjects with baseline values $>$ LLOQ and $<$ ULOQ and post-baseline values \leq LLOQ will be categorized as “decreased from baseline”.

When an improved assay becomes available, all samples may be re-run using the improved assay.

Adverse Events

Adverse events with missing severity will be assigned the highest severity. Adverse events with missing relationship will be assigned the highest relationship.

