5.1.2 Key Secondary Endpoint(s)

- Change from baseline at 18 months in brain amyloid pathophysiology as measured by amyloid PET
- Change from baseline in the derived ADCOMS at 18 months
- Change from baseline in CDR-SB at 18 months
- Change from baseline in ADAS-Cog at 18 months
- Change from baseline in CSF biomarkers (A β [1-42], t-tau, and p-tau) at 18 months
- Change from baseline in total hippocampal volume at 18 months using vMRI

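### Out-of-range post-baseline CSF values are dropped in Section 5.8 and have no stated rule in Section 5.4.4; excluding them selects on the outcome and can bias the treatment difference

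*SAP*

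**What the plan says.** SAP Section 5.3.5 has a short block on CSF biomarkers with four parts:

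- A subject whose baseline value is at or beyond a quantitation limit "will be excluded from all statistical analyses".
- In the exploratory work of Section 5.8, the plan admits "only subjects with post-baseline values" lying strictly inside both limits.
- A further set of analyses retains anyone with a result after baseline, in range or not, and sorts these subjects into three classes: no change, up or down. A result at or above the ULOQ counts as up and one at or below the LLOQ as down. The size of the change plays no part.
- "When an improved assay becomes available, all samples may be re-run using the improved assay". No trigger or date is attached.

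The general paragraph of the same section adds: "Missing values in key secondary endpoints, secondary endpoints and exploratory endpoints related to clinical assessments and biomarkers will be handled by the MMRM".

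Section 5.1.2 lists "Change from baseline in CSF biomarkers" (Aβ[1-42], t-tau and p-tau) at 18 months among the key secondary endpoints. Section 5.1.3 lists the same markers at 12 months as secondary. Both are analysed under Section 5.4.4, whose models "compare the combined 10 mg dose group (including bi-weekly and monthly regimens) with placebo for the key secondary endpoints". Section 5.4.4 does not mention quantitation limits. Section 5.8 is exploratory: it takes CSF change by baseline PET subgroup and relates CSF to clinical endpoints.

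**The concern.** A result beyond a quantitation limit is not an absent result: the assay has shown on which side of the limit it lies. The three-class analysis uses exactly that information, and the numeric analysis in Section 5.8 discards it. If treatment moves a marker toward a limit, more treated than placebo subjects cross it. The subjects removed are then those with the largest changes, and they come disproportionately from the active arms.

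The MMRM does not repair this. It relies on missingness at random given the observed data, whereas here the number is absent because of its own size.

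Section 5.4.4 matters more, because the CSF endpoints there rank higher, yet the rule names only Section 5.8. Whoever programs the 18-month key secondary comparison could exclude the result, set it to missing or substitute the limit, each consistently with the text. These choices give different estimates. The choice should not be open once the data are unblinded.

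**Working it through.** The SAP gives no CSF sample size, effect size, SD, quantitation limit or out-of-range rate, so it has no figure to reproduce. Everything below is illustration. Effects are in SD units, and effect sizes, limits and correlations are assumptions.

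**Step 1: the mechanism, without baseline adjustment.** If Y is normal with mean μ and SD 1, and only values below a limit u are kept, then E[Y | Y < u] = μ − φ(u − μ)/Φ(u − μ). Put 10% of placebo above the ULOQ, so u = 1.282, and take a true shift of 0.5.

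- Placebo: 0 − φ(1.282)/Φ(1.282) = −0.195.
- Active: 0.5 − φ(0.782)/Φ(0.782) = 0.124, with 21.7% of active values dropped.
- Observed difference: 0.124 − (−0.195) = 0.319. Loss: 1 − 0.319/0.5 = 36%.

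Over shifts of 0.25-0.75 SD, the loss is 22-52% with 5-20% of placebo out of range, 8-13% with 1%, and 2-3% with 0.1%.

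**Step 2: closer to the plan.** Step 1 overstates the loss, because the SAP also excludes out-of-range baselines and adjusts for baseline. The simulated model is the ANCOVA that Section 5.4.4 lists beside the MMRM: change on treatment and baseline, one post-baseline visit, out-of-range baselines removed, equal spread. With a true effect of 0.50 and baseline-to-post correlation 0.8 (all values known: 0.501):

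| ULOQ cuts off the upper … of baseline | Out of range, placebo / active | Values dropped | Loss | Values set to the limit |
|---|---|---|---|---|
| 5% | 2.6% / 9.3% | 0.447 | 11% | 0.474 |
| 10% | 4.8% / 15.1% | 0.420 | 16% | 0.454 |
| 20% | 8.9% / 24.1% | 0.383 | 24% | 0.423 |

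Loss is 1 − dropped/0.501. With correlation 0.6 the dropped-value estimates are about 0.41, 0.38 and 0.33, a loss of about 18%, 24% and 34%. Together these give roughly 10-35%. With under 1% of placebo out of range and correlation 0.8, the loss is about 4%. For a true 0.25 SD effect with the limit at 10% and correlation 0.8, the estimate is 0.215 against 0.249, a loss of 14%.

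**Step 3: direction.** With no effect and equal spread, dropping values gives 0.000, so there is no bias. With the active-arm residual SD at 1.5 times placebo:

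- ULOQ at the upper 10%: a true 0 becomes −0.098.
- LLOQ at the lower 10%: a true +0.25 becomes +0.303.

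Bias toward zero is therefore the usual result under a common-spread shift, but not a general one.

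**Step 4: remedies.** A censored-data likelihood, in which an out-of-range result contributes the probability of lying beyond the limit, recovered the all-values estimate to within 0.002 (for example 0.501 against 0.502) when the normal model was correct. Setting values to the limit recovered only part of the loss, as the table shows.

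**The case against.** The strongest reply concerns scope. A reader might infer that the plan drops out-of-range subjects from the key secondary CSF comparison. The text does not say so: the exclusion is tied to the exploratory Section 5.8, and handling in Section 5.4.4 is unstated. That stands, and the point is limited accordingly: an outcome-based exclusion in 5.8 and a missing rule in 5.4.4. A reader might also infer that the rule flattens the CSF dose relationship. That assessment sits in Section 5.5.2, which the rule does not name, and Section 5.5 leaves further details to a separate analysis plan.

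Second, the plan has mitigations. The three-class analysis keeps subjects with out-of-range post-baseline values, so a directional effect can still be seen. It ignores magnitude, however, and cannot stand in for the mean-change comparison. Re-assay is only permitted, so it is not a safeguard.

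Third, size and direction. Attenuation of 36%, or bias that always runs toward zero, is tempting to quote. The first ignores the planned baseline covariate and baseline exclusion. The second fails when the arms differ in spread. Both objections stand. So does the point that the loss is negligible if hardly any value leaves the range.

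The baseline exclusion itself is not at issue: it selects on a pre-treatment value.

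**Conclusion.** The point holds in this form. Section 5.3.5 makes inclusion in the numeric CSF analyses of Section 5.8 depend on the post-baseline value, and leaves out-of-range values in the Section 5.4.4 key secondary and secondary CSF comparisons without a rule. Where such values are excluded or treated as missing at random, the treatment difference can be biased, usually toward zero when the arms have similar spread.

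For a 0.5 SD effect the illustrative loss is about 10-35% with the limit at the outer 5-20% of the baseline distribution, and only a few percent when under 1% of placebo values are out of range. These figures assume normal outcomes, a one-sided limit, equal spread, one post-baseline visit and a baseline correlation of 0.6-0.8. None of these comes from the SAP. Without the out-of-range rate, the actual bias in this trial cannot be sized.

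The primary endpoint is not affected. This is a cheap improvement to the plan, not evidence that the key secondary CSF result is biased.

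**What to change.** Amend the CSF block of Section 5.3.5 so that one rule covers Sections 5.4.4 and 5.8 wherever CSF change is the outcome:

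1. Keep post-baseline values at or beyond a limit as left-censored at the LLOQ or right-censored at the ULOQ, in a censored-likelihood mixed model with the same covariates as the planned MMRM.
2. Report the in-range-only analysis as a sensitivity analysis.
3. Tabulate the number of out-of-range values by marker, arm and visit, so that readers can judge how much the handling matters.

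The baseline exclusion and the three-class analysis can stay. Setting values to the limit and using rank ANCOVA should not be offered as an equal alternative: limit substitution recovers only part of the loss, and rank ANCOVA does not estimate mean change.

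The cost is a few lines of SAP text, modest programming, and reliance on a distributional assumption beyond the assay limits. No extra data are needed.
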